The University of Manchester will be the sponsor of the proposed research. Governance will be provided internally through the existing support systems (e.g. UREC, Research Development Manager, Finances and Accounts, and Research Strategy Group) and independently by the Christie NHS Foundation Trust (UK CRC CTU 9). We will also be held to account by our study Steering Group (made up of senior members of the research team, Christie CTU representative, University of Manchester accountants, NIHR representative, school representatives, relevant charities and voluntary organisations (e.g. Young Minds), parents, young people, and an academic advisor). This group will meet approximately every six months during the course of the study.

Clinical Trials Unit

In general, the CTCU acts as an independent provider of clinical trial services for investigatorled/academic studies undertaken within the Greater Manchester region. These services form part of the research governance that is undertaken on behalf of the (NHS) study sponsor and includes project and grant management, data management, statistical services, trial monitoring and quality assurance. By providing data management/co-ordination and statistical support of research studies, the CTCU adds value to the programme by means of independent data management oversight, development of the research data record forms/CRFs, provision of a robust database for capture of primary research data and provision of independent QA monitoring of the research studies to ensure compliance with national and international regulations such as DoH Research Governance and Good Clinical Practice.

In this particular study, the CTCU will be providing independent project & trial management to ensure that the study is set up and adheres to compliance with the relevant DH research governance framework. This activity includes preparation of the appropriate study master files and protocols and support for ethics body submissions. Support for the in-study phase of the project will include coordination of relevant IDMC and TMG meetings and a degree of study site monitoring, particularly in respect of consent form process. The CTCU will also be providing the study randomisation service

TRIAL MONITORING

Data Collection

Please see 'Trial Methodology' section

Data will be coordinated by [name] - Senior Research Associate. [name] - Principal Investigator, [name] - Research Associate and [name] - Statistician, will also have access to the data for analysis. All of the above members of staff have Criminal Records Bureau clearance at the Enhanced Disclosure level.

Outcome data will be collected via online surveys, however paper copies will be available when necessary. Data security for online surveys will be ensured using hypertext transfer protocol secure (HTTPS) data encryption. Data matching will be achieved through the triangulated use of name, date of birth and UPN, but these will be removed prior to analysis. All qualitative data will be anonymised during the transcription process, with pseudonyms given to any personally identifying information. All data will be held safely on secure drives, with the University of Manchester and Microsoft Best Practice guidelines, and adherence to the Data Protection Act 1998 followed. Data will be held behind both internal and external firewalls, and physical transportation (e.g. on flash drives) will be prohibited.

CONFIDENTIALITY AND DATA PROTECTION

Confidentiality

All data will be kept anonymous and confidential except in the event of a child protection issue (for example, a child disclosing details of abuse during an interview), at which point standard safeguarding protocols will be followed. Data security for online surveys will be ensured using hypertext transfer protocol secure (HTTPS) data encryption. Data matching will be achieved through the triangulated use of name, date of birth and UPN, but these will be removed prior to analysis. All qualitative data will be anonymised during the transcription process, with pseudonyms given to any personally identifying information. All data will be held safely on secure drives, with the University of Manchester and Microsoft Best Practice guidelines followed. Data will be held behind both internal and external firewalls, and physical transportation (e.g. on flash drives) will be prohibited.

Data Protection

The research team will use hypertext transfer protocol secure (HTTPS) data encryption – the same technology used in online banking – to ensure the security of the data collected through the project website. Data matching (e.g. matching up a pupil's Time 1 data with their Time 2 data in order to assess the amount of change that has occurred) will be achieved through the triangulated use of name, date of birth and Unique Pupil Numbers, but these will be removed prior to actual analysis.

All qualitative data will be anonymised during the transcription process, with pseudonyms given to any personally identifying information. Since it will obviously be important for the research team to know who a given transcription relates to, we will keep a master list of the real names for each pseudonym on a

secure drive at the University of Manchester.

All data are to be held safely on secure drives, with the University of Manchester and Microsoft Best Practice guidelines followed. There will be stringent access policies. Data will be held behind both internal and external firewalls. The physical transportation of data (e.g. on flash drives) will be prohibited.

TRIAL CONDUCT

Protocol Amendments

Any changes in research activity (except those necessary to remove an apparent, immediate hazard to the participant) will be reviewed and approved by the Chief Investigator and submitted in writing to the appropriate REC for approval prior to enrolment into an amended protocol.

TRIAL RECORD RETENTION

Trial records will be retained for approximately five years after the conclusion of the study (this is the period of time during which we expect to still be producing outputs that make use of study data).

END OF TRIAL

The Chief Investigator and/or the trial steering committee have the right at any time to terminate the trial for safety or administrative reasons. The end of the trial will be reported to the REC within the required timeframe if the trial is terminated prematurely. Investigators will inform participants of any premature termination of the trial and ensure that the appropriate follow up is arranged for all involved. A summary report of the trial will be provided to the REC within the required timeframe

PEER REVIEW

Internal review was undertaken by colleagues in the School of Education during the drafting process – this led to minor revisions to the proposal. The proposal has been reviewed by the funder (NIHR), including commissioning panel and expert peer review, on several occasions. Suggested amendments were made, reviewed and approved by the funder.

ETHICAL AND REGULATORY REQUIREMENTS

The sponsor will ensure that the trial protocol, participant information sheet, consent form and submitted supporting documents have been approved by the appropriate research ethics committee, prior to any participant recruitment. The protocol and all agreed substantial protocol amendments, will be documented and submitted for ethical approval prior to implementation.

The CI and sponsor will ensure that the REC and are notified that the trial has finished (either as expected or prematurely) within required timeframes with summary reports to be provided as required.

Table 3: Summary of protocol changes and justification

Change	Justification	Page
Health Economist [name]	[name] left the university and was replaced by [name] to complete the health economic analyses	3
Trial objectives Hypothesis 1: Children in primary schools implementing PATHS over a two-year period will demonstrate significant improvements in social skills (1a) and pro-social behaviour (1b); mental health difficulties (specifically internalising symptoms, 1c; and externalising problems, 1d); health-related quality of life (specifically psychological wellbeing, 1e; social support and peers, 1f; and school environment, 1g), exclusions (1h), attendance (1i) and academic attainment (1j), when compared to those children attending control schools.	Hypothesis amended to mirror the specific subscales of the measures used to assess social and emotional competence and health-related quality of life.	10
Trial objectives Hypothesis 2: The effects of PATHS on social skills (2a) and pro-social behaviour (2b); mental health difficulties (specifically internalising symptoms, 2c; externalising problems, 2d); health-related quality of life (specifically psychological wellbeing, 2e; social support and peers, 2f; and school environment, 2g) will be sustained at two-year post-intervention follow- up	Hypothesis amended to specifically reflect availability of data at follow-up and to mirror the specific subscales of the measures used to assess social and emotional competence and health-related quality of life.	10
Trial objectives Hypothesis 3: Children in primary schools implementing PATHS over a two-year period will demonstrate significantly better psychosocial adjustment (specifically, psychological wellbeing, 3a; social support and peers, 3b; and school environment, 3c), upon transfer to secondary school, when compared to those attending control schools.	Hypothesis amended to reflect the specific subscales of the measures used to assess psychosocial adjustment.	10
Trial objectives Hypothesis 4: Variability in the implementation of PATHS (specifically, fidelity, 4a; dosage, 4b; quality, 4c; participant responsiveness, 4d; and reach, 4e) will be significantly associated with variability in intervention outcomes	Hypothesis amended to reflect the specific dimensions of implementation assessed.	10
Trial objectives Hypothesis 5: Social skills and the school environment at T1 will be associated with psychological wellbeing and mental health difficulties (internalising symptoms and externalising problems) at T2, which in turn will predict academic attainment at T3	Hypothesis amended to reflect the specific subscales of measures used in the trial that could be mapped across to the SEL logic model	10
Trial objectives Hypothesis 6: The PATHS curriculum will demonstrate cost-effectiveness.	Addition of the sixth hypothesis assessing the cost- effectiveness of PATHS	10
Opt-out will be used for parental consent (however, this will be repeated at the start of the follow-up phase when the oldest cohort move into secondary school before each wave of data collection).	The initial consent form covered the duration of the main trial. Opt-out consent was repeated ahead of the follow-up phase as pupils had moved into new schools.	12
The baseline assessment of outcomes now takes place prior to randomisation rather than after.	This change was implemented following feedback on a similar trial conducted by Dartington Research Unit, who randomised schools first and immediately lost 8 schools allocated to the control arm of their	12

	trial. We set a minimum threshold in order to ensure	
	that the study baseline would be adequately	
Intervention	The PATHS materials and training are being funded	12
Intervention	by the EEE as noted in our correspondence. This is	12
	a change to the original plan, in which schools	
	themselves would have been required to pay.	
Schools –	Training event reference removed as this is not part	13
2 day training event removed	of the trial methodology, but rather the intervention	
Schools – PATHS co-ordinator Interview (Spring	We interviewed the PATHS co-ordinators at schools	13
2013)	were they were not the year 3, 4, or 5 teacher	
	implementing PATHS, and thus not already being	
	interviewed as part of the teacher interview. For	
	example in cases were they the coordinator was	
	either a Head Teacher, Deputy Head or Key Stage	
Schools -	Two visits to PATHS schools per year were	13
PATHS school visits - Twice a year - 2012/13.	conducted. This was to reduce the burden on	10
2013/14	schools. One year group was the focus of each visit.	
Teachers –	Implementer characteristics survey removed as was	13
Implementer characteristics survey - Autumn 2012	not part of the stated hypotheses.	
Teachers –	The factors affecting implementation survey	13
Factors affecting implementation: barriers and	removed as was not part of the stated hypotheses.	
facilitators survey – Spring 2013, Spring 2014		
Teachers –	Two visits to PATHS schools per year were	13
PATHS school visits - Twice a year - 2012/13,	conducted. This was to reduce the burden on	
2013/14	schools. One year group was the focus of each visit.	10
Pupil outcome survey Summer 2012	The assessment of outcomes has been brought	13
	forward to June/July from September. As noted in	
	schools are less busy in the summer term and also	
	teachers completing surveys will have a much	
	greater knowledge of individual children, having	
	taught them for nearly a full school year (as	
	compared to only a couple of weeks if the surveys	
	were completed in September as originally planned.	
Parent –	Parent informant-report surveys were collected, but	14,
Outcome measures	the response rate was far too low (baseline n=716,	15
	T2 n=444, T3 n=279) to allow meaningful analyses	and
Devel	to take place.	16
Parent –	Parent interviews were added to i) explore parental	14
Interviews Spring - 2014	perceptions, understanding, knowledge,	
	engagement and involvement in FATHS, and if) to explore perceptions of effectiveness of PATHS	
	Working with the schools, a selection of parents	
	were contacted, with a focus on parents of pupils	
	with EAL, SEND and FSM.	
Pupils –	Pupil focus groups were added to i) explore pupil	14
Focus groups Spring - 2014	responsiveness to and engagement with PATHS, ii)	
	explore generalisation of concepts/strategies, iii)	
	explore 'fit' with English educational context, and vi)	

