- Short title: PATHS to Success
- **Design:** Cluster randomised controlled trial
- **Objectives:** The primary aim of the trial is to examine the impact of the PATHS curriculum on the social and emotional wellbeing of children in primary schools in England, with the following objectives:

Primary Objective:

• To determine the impact of PATHS on a variety of outcomes for children, i.e. social skills

Secondary Objectives:

- To determine whether the impact of PATHS is sustainable
- To determine the impact of PATHS on children's psychosocial adjustment to secondary school
- To assess the role of implementation variability in moderating the impact of PATHS on outcomes for children
- To assess the validity of the logic model for SEL programmes
- To examine the cost-effectiveness of PATHS

Endpoints:

Primary Endpoint:

• Children in primary schools implementing PATHS will demonstrate significant improvements in social skills

Secondary Endpoints:

- The sustainability of the effects of PATHS for a 2 year follow up period
- Children in schools implementing PATHS will demonstrate significantly better psychosocial adjustment upon transfer to secondary school, compared to those attending control schools
- Quality of implementation will be associated with improved outcomes in schools implementing PATHS
- Social skills and the school environment at T1 will be associated with psychological wellbeing and mental health difficulties (internalising symptoms and externalising problems) at T2, which in turn will predict academic attainment at T3
- The PATHS curriculum will demonstrate cost-effectiveness.

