Our proposed research will build upon what is already known in the field and address the specific gaps outlined above. In doing so, it will provide major advances in the theory, research and practice of promoting social and emotional wellbeing in primary education. In response to the commissioned call from the National Institute for Health Research (NIHR), we have selected an intervention that is appropriate to the topic (social and emotional wellbeing) and context (primary school) outlined, and is thoroughly grounded in rigorous research.

Assessment and management of risk

The design of the proposed research minimises the risk of harm to participants. As a failsafe, members of our research team will have reviewed participating schools' health and safety protocols and will act accordingly in the event of such an incident. In terms of emotional harm, in the event of a participant becoming upset or distressed at any point in the research, the researcher will immediately cease data collection and contact an a-priori nominated member of school staff to provide support. Preventive measures will also be in place – for example, contact details of organisations who can provide independent support and advice on social and emotional issues (e.g. Childline) will be made available to all participants.

As the project is school-based and focuses upon pupil outcomes it is inevitable that children under 16 will be sampled. All members of the research team have completed full CRB enhanced disclosure and will be briefed on LA Child Protection protocols. Parental consent will be sought for all participants

TRIAL OBJECTIVES

1. To determine the impact of PATHS on a variety of outcomes for children

Hypothesis 1: Children in primary schools implementing PATHS over a two-year period will demonstrate significant improvements in social skills (1a) and pro-social behaviour (1b); mental health difficulties (specifically internalising symptoms, 1c; and externalising problems, 1d); health-related quality of life (specifically psychological wellbeing, 1e; social support and peers, 1f; and school environment, 1g), exclusions (1h), attendance (1i) and academic attainment (1j), when compared to those children attending control schools.

2. To determine whether the impact of PATHS is sustainable

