The proximal impact of the PATHS curriculum is on children's social and emotional competence. Recent systematic reviews of measures in this area ^(46, 48) highlighted the *Social Skills Improvement System* (SSIS) rating scales and the *Strengths and Difficulties Questionnaire* (SDQ) as being among the 'gold standard' instruments. The SSIS provides measurement of social skills (including communication, empathy, and self-control), problem behaviours (including internalising and externalising difficulties) and academic competence (including reading and maths achievement¹, and motivation to learn). The measure (previously known as the Social Skills Rating System – SSRS) is well established in the academic literature, having been included in excess of 40 research articles published in peer-reviewed journals. It has child, teacher and parent-rated versions, takes approximately 15-25 minutes to complete, and has been standardised for children and young people aged 3-18 (child-rated version from age 8). The rating scales follow a Likert response format in which raters read a statement (an example from the teacher-rated version is, "[This child] shows concern for others") and indicate their level of agreement on a four-point scale. The SSIS rating scales have excellent psychometric properties, as detailed below:

- Reliability
 - Internal: co-efficients range from 0.72-0.95
 - Test-retest: co-efficients range from 0.72-0.92
 - Inter-rater: co-efficients range from 0.48-0.69
- Validity
 - Factorial: established through confirmatory factor analysis (CFA)
 - Convergent: correlates with a range of similar instruments (e.g. BASC-2)
 - Discriminative: discriminates between clinical (including children with ADHD, behavioural, emotional and social difficulties, and learning difficulties) and non-clinical samples
- Other
 - Development and subsequent refinement of the SSIS utilized Item Response Theory⁽⁴⁶⁾

¹ Teacher informant report version only.

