The SDQ provides measurement of children's internalising symptoms (emotional symptoms and peer problems), externalising problems (conduct problems and hyperactivity/inattention), and pro-social behaviour. It is the most widely used outcome measure of its type in the UK. Teacher informant-rated versions are available for children under the age of 11, which take approximately 5-10 minutes to complete. The SDQ follows a Likert response format in which raters read a statement (an example from the parent-rated version is, "[This child] often lies or cheats") and indicate their level of agreement on a three-point scale. The SDQ has strong psychometric properties, as detailed below:

- Reliability
 - Internal: co-efficients range from 0.57-0.87
 - Test-retest: co-efficients range from 0.61-0.80
 - Inter-rater: co-efficients range from 0.27-0.48
- Validity
 - Factorial: established through exploratory factor analysis (EFA)
 - Convergent: correlates with a range of similar instruments (e.g. CBCL)⁽⁵⁴⁾
 - Predictive: strongly predictive of independently diagnosed psychiatric disorders

In view of the overlap between elements of the SSIS and the SDQ and to reduce the data collection burden for respondents, we propose to strategically select subscales from these instruments. So, for example, given that the SSIS externalising difficulties subscale and SDQ externalising problems subscales essentially tap the same domain, we propose to use only the latter in our teacher surveys. Full clarification of the subscales that will be used with each informant (child, teacher) can be found in Table 2 below.

Secondary outcome measures

Health-related quality of life

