All schools in England record data on attendance, attainment and exclusions for each of their pupils and it is held at both local (e.g. LA) and national (e.g. Department for Education – National Pupil Database (NPD)) levels. We will intercept the data as required at the LA level, reducing the data collection burden on schools involved in the trial. *Attendance* data is recorded as the proportion of half-days missed due to unauthorised absence. Changes in children's *academic attainment* will be assessed in two ways – firstly, via end of Key Stage 2 points scores for Maths and English. These point scores are derived from the National Curriculum levels attained by children in their Key Stage 2 Standard Assessment Tests (SATs), which are completed at the end of Year 6. For *exclusions*, we will record the frequency of both permanent and fixed-term exclusions for each participant during the course of the trial. For the latter we will also record the duration of the exclusion period (number of days).

Psychosocial adjustment to secondary school

Children's adjustment to secondary school will be assessed by utilising key subscales from the KS-27. These are:

- o School environment
- Peers and social support
- Psychological wellbeing

Table 2: Summary of outcome measures

Measu	res	Child	Teacher	
Primary outcome measure	Social and emotional competence	Social skills (SSIS)	Pro-social behaviour (SDQ) Internalising symptoms (emotional symptoms and peer problems) (SDQ) Externalising problems (conduct problems and hyperactivity/inattention) (SDQ)	
me measures	Health-related quality of life	CHU-9D Psychological well-being (KS-27) Social support and peers (KS-27) School environment (KS-27)		
dary outco	Psychosocial adjustment to secondary school	Psychological well-being, social support and peers, school environment (KS-27)		
Secon	Attendance, attainment and exclusions	Attainment derived from NPD I records.	Key stage 1 and 2. All other measu	res to be derived from LA/NPD

STATISTICS AND DATA ANALYSIS

Trial Design

Cluster-randomised controlled trial.

Sample size calculation

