We anticipate an effect size of at least d=0.2 for our primary outcome measure. With an estimated ICC of at most 0.05, and an average cluster size of N=75 (3 classes x 25 participants), we require 50 clusters (schools) (25 in each arm of the trial) with the standard thresholds of Power at 0.8 and Alpha at 0.05. This would yield a total sample size of 75 x 50, N = 3,750 (see supporting documentation SD1 CONSORT for flow of participants through the study). As noted above, this is a purposefully conservative estimate; in most published research, the ICC for psychosocial outcome variables in primary schools typically ranges from 0.03 to <0.01, and the effect sizes for outcome measures in PATHS trials have been close to d=0.5 in some cases(26[,] 25), with most falling into the 0.3-0.4 range. Based on this, we believe that the effect size is most likely to be around d=0.3, and the ICC is most likely to be around 0.02. With Power at 0.8 and Alpha at 0.05, and the same cluster size, we would need 12 clusters (6 in each arm of the trial), yielding a total sample size of 75×16 , N = 900. However, the larger sample noted above helps to support analyses where the overall dataset will be stratified into subgroups at school and/or pupil level. As there will be several of these instances in the study (e.g. H3 adjustment to secondary school, H4 – implementation variability), the retention of a large sample of schools/pupils will optimise power for the ensuing analyses. For example, Hypothesis 3 will be tested using data from the N=1,250 children who have transferred to secondary school at the crossover point of the trial (the start of the 2014/15 school year). As a failsafe, in the event of a reduced effect size of <0.3 or inflated ICC of >0.02, we could of course continue to take outcome measures for the N=1,250 children who transfer to secondary school the year after (e.g. at the start of the 2015/16 school year), doubling the sample size for this analysis².

² Although this will shorten the period during which adjustment to secondary school can be measured to one year rather than two (since the trial will conclude at the end of the 2015/16 school year).

TRIAL MANAGEMENT AND OVERSIGHT ARRANGEMENTS

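### The synopsis names social skills as the one primary endpoint, but the outcome-measures text and Table 2 make four scores primary; the stated alpha and power fit only the single-endpoint reading.

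*Protocol*

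**What the plan says.** Four places in the protocol bear on which result decides the trial.

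- **Synopsis, Objectives and Endpoints.** The primary objective reads "To determine the impact of PATHS on a variety of outcomes for children, i.e. social skills". The single primary endpoint reads "Children in primary schools implementing PATHS will demonstrate significant improvements in social skills". The secondary endpoints do not list the SDQ scores as between-arm effects in their own right.
- **Primary outcome measure (Social and emotional competence).** This section starts from a construct: "The proximal impact of the PATHS curriculum is on children's social and emotional competence". It describes both the SSIS and the SDQ under the primary heading and then defers to the table: "Full clarification of the subscales that will be used with each informant (child, teacher) can be found in Table 2 below".
- **Table 2, primary row.** The child column has "Social skills (SSIS"). The teacher column has three scores: "Pro-social behaviour (SDQ) Internalising symptoms (emotional symptoms and peer problems) (SDQ) Externalising problems (conduct problems and hyperactivity/inattention) (SDQ").
- **Sample size calculation.** It speaks of one outcome without naming it: "We anticipate an effect size of at least d=0.2 for our primary outcome measure". It uses an ICC of at most 0.05, 75 pupils per school, alpha 0.05 and power 0.8, and arrives at 25 schools per arm.

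Hypothesis 1 under Trial Objectives lists ten outcomes, 1a to 1j, without marking one as primary; it begins with children who "will demonstrate significant improvements in social skills (1a) and pro-social behaviour (1b").

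**The concern.** A reader of the synopsis finds one primary endpoint. A reader of the measures section and Table 2 finds four. Both are current text, and nothing says whether any one of the four, all of them, a composite or an ordered sequence decides success. The alpha and power in the sample size section can be true of only one of these readings.

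This matters most if the results disagree. If social skills shows no effect and one SDQ score does, Table 2 would allow the SDQ result to be reported as primary and the synopsis would not.

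The three disputed scores may also be the more exposed to rater bias. Class teachers deliver PATHS, and teachers complete the SDQ. It is a reasonable inference that in the PATHS arm the T2 and T3 raters are the class teachers who give the lessons and know the allocation.

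**Working it through.** **1. The plan's own figure.** Inputs from the sample size section: d=0.2 (SD 1), ICC 0.05, 75 pupils per school, alpha 0.05, power 0.8. Sidedness is not stated.

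- Pupils per arm before clustering, two-sided: 2 × (1.960 + 0.842)² / 0.2² gives 393.
- Design effect: 1 + (75 − 1) × 0.05 = 4.70.
- Schools per arm: 393 × 4.70 / 75 = 24.6, so 25. Total: 50 schools, 50 × 75 = 3,750 pupils.

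This matches the protocol. A one-sided test would need 20 schools per arm, so the stated figure is that of one outcome tested two-sided at 5%.

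**2. Power at 25 schools per arm, one outcome.** SE = √(2 × 4.70 / 1,875) = 0.0708, and 0.2 / 0.0708 = 2.825. Power is 80.6% by the normal approximation and 79.0% by t with 48 df.

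**3. Four primary scores, each at 5%, any one counting.** If independent, the chance of at least one false positive is 1 − 0.95⁴ = 18.5%. For correlated scores, simulation (1,000,000 draws, common pairwise correlation) gives:

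| Assumed correlation | At least one of four, two-sided 5% |
|---|---|
| 0.3 | 17.4% |
| 0.5 | 15.6% |
| 0.7 | 13.1% |
| 0.9 | 9.4% |

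Counting only false positives in favour of PATHS, the range is 9.6% (independent) to 4.7% (correlation 0.9), against 2.5% for a single test.

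**4. Four primary scores with a Bonferroni split.** Each is tested at 0.05 / 4 = 0.0125.

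- At d=0.2 and ICC 0.05, power per score is 62.8% (normal) or 59.3% (t, 48 df). Restoring 80% needs 558 × 4.70 / 75 = 34.97, so 35 schools per arm: 70 schools, 5,250 pupils.
- At d=0.3 and ICC 0.02, the design effect is 1 + 74 × 0.02 = 2.48, SE = √(2 × 2.48 / 1,875) = 0.0514, and 0.3 / 0.0514 is about 5.83. Power per score at 0.0125 is above 99%.

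**5. All four required, each at 5%.** At d=0.2 and ICC 0.05 for every score, joint power is 42% if independent and 51–71% at correlations of 0.3–0.9.

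The documents give no correlations between the scores. These, and a common d and ICC for all four, are assumptions.

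**The case against.** The best defence is that the synopsis is where endpoints are defined, that it singles out social skills, and that the sample size section speaks of one primary outcome measure. On this view Table 2 only summarises instruments by construct and informant, and the measures text defers to it for subscales, not for a testing order. This has force: it shows which reading the sponsor probably intended. It does not remove the conflict, because the row is labelled as the primary outcome measure and nothing in the synopsis moves the SDQ scores to secondary.

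Some stronger readings are tempting, and the protocol does not support them.

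- **That the trial has no single 5% test anywhere, or that nothing ranks the four scores.** The synopsis does rank them, and under it the single test exists.
- **That Hypothesis 1 makes ten outcomes primary.** Table 2 puts the other six (three KS-27 domains, exclusions, attendance, attainment) among the secondary measures.
- **That the time point is open.** Hypothesis 1 concerns implementation over two years and T3 is the end of that period, so T3 is the natural reading, although no sentence labels it primary.
- **That the real error rate is 18.5%.** This needs an any-one-of-four rule that the protocol never adopts, and independence, which is implausible for three subscales completed by the same rater. A multiplicity rule may also stand in the SAP, which is not shown; its absence from the protocol is not the point here.
- **That the trial is underpowered.** The loss appears at values the protocol calls deliberately conservative and vanishes at those it thinks most likely.
- **That the SDQ raters are stated to be the deliverers.** They are not. The remark in the table of protocol changes about teachers who know the children well concerns the baseline survey, which precedes randomisation, and control teachers do not deliver PATHS.

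Two limits on the child-rated SSIS also stand. The children receive the lessons and are not shown to be blinded. The child version is standardised from age 8 while eligibility starts at 7, although a child aged 7 at entry is past 8 by T3.

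**Conclusion.** The point holds as a contradiction within current protocol text: one primary endpoint in the synopsis, four primary scores in the measures section and Table 2, and no rule joining them. The sample size is correct for a single outcome, and alpha 0.05 with power 0.8 is true only under the synopsis reading.

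The statistical cost of the four-score reading is conditional. It depends on a success rule the protocol does not give, on assumed correlations, and on which of the protocol's two pairs of d and ICC applies. Teacher-rater bias is an added reason to settle the SDQ scores' status, resting on inference. What is certain is that the document that must say which result decides the trial gives two answers.

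**What to change.** Align Table 2 and the primary outcome measure section with the synopsis. State that the sole primary outcome is child-rated SSIS social skills at T3, the end of the two-year intervention, compared between arms at two-sided 5%. Move the three teacher-rated SDQ scores to the secondary rows, with a note that in the PATHS arm the raters are likely to be unblinded class teachers delivering the programme. Name social skills in the sample size section.

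This is a table edit and a few sentences. It needs no new data and no more schools. The cost is that SDQ results can no longer be called primary.

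If the sponsor prefers to keep all four as primary, the protocol must state the decision rule and restate alpha and power to match, with the sample size reconsidered at the planning values.
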